### Analysis

The proportion of subjects not in need of mechanical ventilation (either invasive or non-invasive) at any point during the study treatment period will be analysed using a logistic regression model. The model will be fitted with ventilation required (Yes/No) as the dependent variable and study treatment as a fixed effect. The number and percentage of subjects not requiring ventilation, together with the proportion of subjects not requiring ventilation and the Clopper-Pearson 90% CI for the proportion, will be presented for each dose group. The odds ratio, associated 90% CI and two-sided p-value will also be presented.

### Imputation

Where subjects have been withdrawn from treatment for a reason other than need for mechanical invasive or non-invasive ventilation or death, and have not recorded requirement for mechanical invasive or non-invasive ventilation or death during the time from last treatment administration + 12 hours, they will be considered not in need of mechanical ventilation during the treatment period. All subjects who commence treatment will have an End of Treatment eCRF page completed indicating whether or not the subject was withdrawn due to need for mechanical ventilation or death. Therefore, no further imputation is required.

### Summaries

The ventilation requirements, including the date and time the decision was made, the date and time the ventilation started and the date and time the ventilation stopped or if the ventilation was ongoing will be listed.

### Sensitivity Analysis

A sensitivity analysis will be performed including any additional information gathered between the last study treatment administration and Visit 9 (follow-up period), therefore this analysis will include all data collected from the first treatment administration to the date of study completion or withdrawal. The need for mechanical ventilation is not captured during the follow-up period however the start time of any mechanical ventilation is captured. Therefore, the sensitivity analysis will consider a subject to need mechanical ventilation during the study if any of the following are recorded from the date and time of first study treatment administration to the date of study completion/withdrawal:

- withdrawal from treatment with the reason for withdrawal recorded as need for mechanical invasive or non-invasive ventilation,
- any entry on the Mechanical Ventilation eCRF page indicating that ventilation was required,
- death as recorded on the adverse event or withdrawal from study pages.

The logistic regression model described above will be repeated.

#### **6.10.2.4 Time to Need of Mechanical Invasive or Non-Invasive Ventilation**

Time to need of mechanical ventilation (invasive or non-invasive) for each subject is calculated in hours as (Date and time of decision for need of ventilation) – (Date and time of first administration of study treatment). The treatment period for each subject is from the date and time of their first study treatment administration to the date and time of their last study treatment administration + 12 hours. For subjects who withdraw from treatment with the reason for withdrawal as need for mechanical invasive or non-invasive ventilation, the date and time of decision for need of ventilation is taken from the date and time at which the subject withdrew from treatment (as recorded on the End of Treatment page of the eCRF). For subjects who do not withdraw from treatment due to need for mechanical invasive or non-invasive ventilation but who have an entry on the Mechanical Ventilation eCRF page indicating that ventilation was required during the treatment period, the start date and time from this page will be used to calculate time to need of ventilation. For subjects who do not record a need for ventilation but die during the treatment period, the date and time of death as recorded on the Adverse Event page will be used to calculate the time to need of ventilation.

For subjects not requiring ventilation during their treatment period and who do not die during the treatment period, the time to need of mechanical ventilation will be right censored at the date and time of treatment completion + 12 hours. For subjects who withdraw from treatment for reasons other than need for ventilation or death, the time to need of ventilation will be right censored at the date and time of withdrawal from treatment + 12 hours. The date and time of last treatment administration + 12 hours is a censoring event, should a subject be assessed as having need for ventilation after this time it will be disregarded in the analysis.

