### **6.10.2.3 Number of Subjects Not in Need of Mechanical Invasive or Non-Invasive Ventilation**

The decision for a subject's need for mechanical ventilation (invasive or non-invasive) during the treatment period will determine their response for use in this analysis, irrespective of whether they subsequently received ventilation. A subject will be considered to need mechanical ventilation during the treatment period if they are withdrawn from treatment with the reason for withdrawal recorded as need for mechanical invasive or non-invasive ventilation or death. Any mechanical invasive or non-invasive ventilation or death recorded in the time between last treatment administration + 12 hours will also be considered an event. The treatment period for each subject is from the date and time of their first study treatment administration to the date and time of their last study treatment administration + 12 hours.

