## Sensitivity Analysis

The analysis will be repeated to include subjects who record the need for mechanical ventilation or death between the last study treatment administration and Visit 9 (follow-up period), therefore this analysis will include all data collected from the first treatment administration to the date of study completion or withdrawal to further support the results of the study. For subjects who do not record the need for mechanical ventilation or death during the treatment period, but do record one or both of these during the follow-up period, the earliest of the following will be used to calculate the time to need of ventilation: start time and date as entered on the mechanical ventilation eCRF page or time and date of death as entered on the adverse events page. For subjects who do not record a need for ventilation and who do not die at any point following first study treatment administration, the time to need of ventilation will be right censored at the date of withdrawal from study or study completion.

It should be noted that the decision time is used for subjects who record withdrawal due to mechanical ventilation but the start time of mechanical ventilation will be used for subjects who do not withdraw due to mechanical ventilation but do record an entry on the mechanical ventilation eCRF page.

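### SAP 6.10.2.4 conflicts with 6.10.2.3 on ventilation or death withdrawals after last dose + 12 h and gives two censoring times; the oxygen-day endpoint lacks a sensitivity analysis and one declared change

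*SAP*

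**What the plan says.** **Binary ventilation endpoint (SAP 6.10.2.3).** The qualifying withdrawal reasons are ventilation and death: "A subject will be considered to need mechanical ventilation during the treatment period if they are withdrawn from treatment with the reason for withdrawal recorded". A further sentence adds, as an extra route, ventilation or death recorded up to 12 hours after the last dose. The Imputation paragraph relies on every treated subject having an End of Treatment page "indicating whether or not the subject was withdrawn due to need for mechanical ventilation or death", and concludes that nothing more needs imputing.

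**Time to ventilation (SAP 6.10.2.4).** A ventilation withdrawal is timed at the moment of withdrawal on the End of Treatment page, and that sentence states no limit. Deaths are handled under a narrower condition: "For subjects who do not record a need for ventilation but die during the treatment period". The treatment period ends at last dose + 12 h. Withdrawals for other reasons have their own rule: "the time to need of ventilation will be right censored at the date and time of withdrawal from treatment + 12 hours". A rule for everyone then closes the section: "The date and time of last treatment administration + 12 hours is a censoring event", and "should a subject be assessed as having need for ventilation after this time it will be disregarded in the analysis".

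**Sensitivity analyses of the two ventilation endpoints.** Both reach to the end of the study. In 6.10.2.3 the later events include "death as recorded on the adverse event or withdrawal from study pages". In 6.10.2.4 the repeat runs to Visit 9: "The analysis will be repeated to include subjects who record the need for mechanical ventilation or death between the last study treatment administration".

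**Oxygen days (SAP 6.10.2.5).** The score is the number of days on oxygen from Visit 2 to Visit 8 (0 to 7), compared by a Wilcoxon rank sum test. After ventilation or death on treatment, oxygen is assumed from that day through Visit 8; earlier days stay as recorded. Other gaps take the most recent oxygen status. SAP 6.12 declares that ventilated subjects are now included. Protocol 13.3.1 instead assumes oxygen need for subjects who leave the trial.

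**The concern.** The two ventilation analyses describe the same occurrence, so their event counts should agree. As written, a subject whose treatment was stopped because ventilation was needed can be a failure in one table and censored in the next. That censoring happens shortly before a known failure and because of how dosing ended, so it is not independent of outcome. The second censoring time adds a choice that a programmer would have to make unaided.

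In the oxygen-day test, fewer days rank as better. Once ventilated subjects were brought in, a subject who deteriorated late could rank ahead of one who recovered. Unlike the ventilation endpoints, this section has no sensitivity analysis that would show it.

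**Working it through.** The documents give no power or event rate for these endpoints. The only power figure is for CRP (SAP 3), and it reproduces: 25 / (60 × √(2/75)) = 2.55; 2.55 − 1.645 = 0.91; power 0.82 against about 80%. It does not bear on this point.

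**1. Event rule for a withdrawal from treatment later than last dose + 12 h**

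| Reason | 6.10.2.3 (logistic) | 6.10.2.4 (log-rank) |
|---|---|---|
| Ventilation | Event, by reason alone | Timing sentence: event at withdrawal. Closing sentence: disregarded |
| Death | Event, by reason alone | Outside the treatment period, so not an event |

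Illustration: last dose at hour 64, withdrawal for ventilation 14 h later. Decision time is 64 + 14 = 78 h; cut-off is 64 + 12 = 76 h. Since 78 > 76, the closing sentence removes the event that 6.10.2.3 counts. A death at hour 78 that ends treatment is treated the same way.

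This can arise with no dose missed. Protocol 7.4 specifies a morning and an afternoon or evening dose without clock times. Assume, for illustration only, a first dose at 08:00:

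| Second dose (assumed) | Overnight gap | Hours beyond last dose + 12 h |
|---|---|---|
| 14:00 | 18 h | 6 |
| 16:00 | 16 h | 4 |
| 18:00 | 14 h | 2 |
| 20:00 | 12 h | 0 |

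These are hours of clock time, not a share of events.

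**2. Censoring time for other-reason withdrawals**

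Let L be the last dose and W the withdrawal. The two rules give W + 12 and L + 12, so they differ by W − L. With L = 64 and W = 78 the times are 90 h and 76 h, 14 h apart. Under the first rule the subject stays in the risk set from hour 76 to hour 90, although any need found in that interval would be disregarded. On the assumed schedules, the difference is up to 18, 16, 14 or 12 h if withdrawal is recorded before the next dose is due.

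**3. Oxygen-day score**

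Failure on treatment on day f (1 to 7), with k oxygen days before it (0 to f − 1), scores k + (8 − f). A recovery with oxygen on the first r days (0 to 6) scores r.

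- Ventilation on day 7, no earlier oxygen: 0 + 1 = 1. Recovery after 4 oxygen days: 4. The failure ranks better.
- Ventilation on day 6, no earlier oxygen: 0 + 2 = 2, better than recoveries with 3 to 6 oxygen days.
- Continuous oxygen up to failure: (f − 1) + (8 − f) = 7. Never ranked better.

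A reversal requires k + 8 − f ≤ 5, that is, at least two oxygen-free days before failure (f − 1 − k ≥ 2), and so failure on day 3 or later. Subjects without oxygen at baseline are expected (SAP 6.10.6), so the pattern is possible.

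**4. Departure from the protocol**

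For a subject who leaves the trial off oxygen on day s (1 to 6), for a reason other than ventilation or death, protocol 13.3.1 adds 7 − s oxygen days (6 down to 1). SAP carry-forward adds 0. For a subject on oxygen at that point, both rules add the same. SAP 6.12 lists three changes, and this is not among them.

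**The case against.** **6.10.2.4 does answer the question.** A reader might infer that the section simply leaves late withdrawals undefined. The text does not support that. Read literally, it excludes need assessed after last dose + 12 h, and it confines deaths to the treatment period. What stands is the conflict with 6.10.2.3. For ventilation there is also an internal tension: the timing sentence has no limit, and the withdrawal + 12 h rule exempts ventilation and death withdrawals, as if they were meant to be events. For death there is no such tension within 6.10.2.4.

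**6.10.2.3 also speaks of the treatment period.** One could argue that its withdrawal rule is limited too. However, it presents the 12-hour window as an additional route to an event, and its Imputation paragraph reads the event from the withdrawal reason.

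**No effect on the log-rank test is shown.** Moving a censoring time matters only if another subject's event falls in the interval. This stands.

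**The oxygen score measures what it names.** A subject ventilated on day 7 without earlier oxygen has one oxygen day. Failure is tested in 6.10.2.3 and 6.10.2.4, and 6.10.2.2 scores it as needing oxygen. Oxygen days in follow-up are also summarised. This stands, and it is why the day count should remain the main analysis.

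**Tempting extensions.** A reader might count how many score patterns reverse and take that as a measure of impact. Such counts weight every pattern equally, and the documents give no rates. A reader might also see ambiguity over whether the death rule in 6.10.2.5 means treatment or study withdrawal. It follows directly on the treatment-withdrawal rule as its parallel, and 6.10.2.2 uses treatment withdrawal, so that is the natural meaning.

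**Conclusion.** The rules conflict and need reconciling. The same late withdrawal for ventilation or death is an event in one main analysis and, taken literally, a non-event in the other. Other-reason withdrawals have two incompatible censoring times. The oxygen-day reversal is arithmetically right but conditional on at least two oxygen-free days before failure, and it justifies a sensitivity analysis only. The undeclared departure from protocol 13.3.1 is real and minor.

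The frequency of any of these and their effect on a test result cannot be computed from the documents. The hours shown rest on assumed dose times. Nothing here supports a claim that one arm is favoured. SAP 6.10.4 makes these secondary endpoints descriptive, the CRP primary is unaffected, and the sensitivity analyses of both ventilation endpoints already capture later ventilation and death. The point should be fixed, but it does not threaten the trial's main conclusion.

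**What to change.** - **SAP 6.10.2.4, events.** State that withdrawal from treatment for ventilation or death is an event, as in 6.10.2.3, timed at the recorded withdrawal time for ventilation and at the time of death for death. Limit the closing exclusion to other subjects. Applying last dose + 12 h strictly in both endpoints would also be consistent, but it would drop a ventilation withdrawal made before the next dose is due and keep the informative censoring.
- **SAP 6.10.2.4, censoring.** Use last dose + 12 h as the single censoring time for all subjects without an event.
- **SAP 6.10.2.5.** Keep the day count as the main analysis. Add a sensitivity Wilcoxon test that ranks subjects ventilated or dead between Visit 2 and Visit 8 worse than 7 days.
- **SAP 6.12.** Declare that carrying oxygen status forward for trial withdrawals for reasons other than ventilation or death departs from protocol 13.3.1. Keep discharge separate: protocol 5.4.1 makes it a reason to stop IMP, not to leave the trial.

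The cost is SAP wording and programming before unblinding, with no new data. The drawback is that the added oxygen test is a composite and overlaps 6.10.2.3, so it should be labelled as such.

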### Analysis

A log-rank test will be performed to compare the time to need of ventilation for each of the study treatments.

### Imputation

Dates will be imputed as described above.

## Summaries

Descriptive statistics will be presented for the time to need of ventilation by study treatment. The number and percentage of subjects that are censored will be summarised, along with KM estimates for the 25th, 50th and 75th percentiles of time to need of ventilation and corresponding 90% CIs. The time to need of ventilation will also be presented graphically using a KM plot.

## Sensitivity Analysis

The analysis will be repeated to include subjects who record the need for mechanical ventilation or death between the last study treatment administration and Visit 9 (follow-up period), therefore this analysis will include all data collected from the first treatment administration to the date of study completion or withdrawal to further support the results of the study. For subjects who do not record the need for mechanical ventilation or death during the treatment period, but do record one or both of these during the follow-up period, the earliest of the following will be used to calculate the time to need of ventilation: start time and date as entered on the mechanical ventilation eCRF page or time and date of death as entered on the adverse events page. For subjects who do not record a need for ventilation and who do not die at any point following first study treatment administration, the time to need of ventilation will be right censored at the date of withdrawal from study or study completion.

It should be noted that the decision time is used for subjects who record withdrawal due to mechanical ventilation but the start time of mechanical ventilation will be used for subjects who do not withdraw due to mechanical ventilation but do record an entry on the mechanical ventilation eCRF page.

### **6.10.2.5 Time on Oxygen Supply**

The time on oxygen supply is defined as the number of calendar days on which a subject was recorded as receiving oxygen on the Supplemental Oxygen eCRF page from Visit 2 to Visit 8. For subjects who do not complete treatment, the assessments up to and including the day of the last study treatment administration will be considered and remaining assessments will be imputed as described below. Therefore, a discrete number of responses are available from 0 days to 7 days. Subjects are deemed to have received oxygen where it has been administered at any time for any duration on the date of each visit.

## Analysis

A comparison between the two study treatments will be performed using a Wilcoxon rank sum test. A two-sided p-value of the treatment difference will be presented.

## Imputations

The treatment period for each subject is defined as from the date of first study treatment administration to the date of last study treatment administration. Where subjects have been withdrawn from treatment with the reason for withdrawal recorded as need for mechanical invasive or non-invasive ventilation, or they record need for ventilation (per the mechanical ventilation eCRF page) on the day of last study treatment administration, they will be assumed to require oxygen for the day of withdrawal / last study treatment administration and all subsequent visits up to and including Visit 8 regardless of the oxygen requirement information entered into the Supplemental Oxygen eCRF page. Similarly if a subject withdraws due to death or dies on the day of last study treatment administration they will be assumed to require

oxygen for the day of death and all subsequent visits up to and including Visit 8 regardless of the oxygen requirement entered into the Supplemental Oxygen eCRF page. Otherwise, if a subject has missing assessments for any other reason, their last known oxygen status prior to the missing assessment will be carried forward for the analysis. For subjects who have no post-baseline assessments, no imputation will be applied and they will be excluded from the analysis.

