#### Imputation

For subjects who have withdrawn from treatment due to a need for mechanical ventilation or due to death, or who require mechanical ventilation or die on their last day of study treatment administration, they will be assumed to require oxygen regardless of the oxygen requirement entered into the Supplemental Oxygen eCRF page. For subjects who withdraw from treatment for any other reason, their oxygen status on the last day of study treatment administration according to the Supplemental Oxygen eCRF page will be used. For subjects who have missing data not due to

withdrawal from treatment, their last known oxygen status prior to the missing assessment will be carried forward. For subjects who have no post-baseline assessments, no imputation will be applied and they will be excluded from the analysis.

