### Summaries

The number of days supplemental oxygen is required during screening, the treatment period and the follow-up period will be summarised categorically by treatment. The oxygen requirement for each day will be listed with the imputed oxygen status determined for the end of the treatment period.

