3.8 Rationale for Dose and Dosing Regimen

C21 is being developed for oral treatment of COVID-19. COVID-19 is a viral infection that spreads easily and may cause severe respiratory illness that is potentially life-threatening and represents a huge challenge to the health care system.

The results of the phase 1 healthy subject trials for C21 (C21-003; preliminary data) indicate an acceptable safety and tolerability profile for the 100 mg b.i.d. dose. The risks of C21 in adults are considered primarily related to reversible alopecia seen at the higher dose of 200 mg b.i.d. In the recent phase 1 trial, the 100 mg b.i.d. dose administered for 8 days did not cause any hair loss. Alopecia is therefore not considered to present any significant safety risk to subjects in this trial.

In the recent phase 1 trial (C21-003), 100 mg b.i.d dosing prolonged the duration of the plasma concentration at the rapeutic relevant levels. After oral administration, C21 was rapidly absorbed. On day 8, median t_{max} was 0.33 hours after each dose post-dose, and C21 was only measurable in plasma until 4-6 hours after the first and second dose. Lower doses than 100 mg b.i.d. may not provide maximal efficacy benefit.

Vicore Pharma AB Version: 2.0 Trial ID: VP-C21-006 Date: 14-Aug-2020

The most recent information on the natural course of hospitalised COVID-19 patients, indicate that these patients generally deteriorate within 48 hours and are either discharged or taken into intensive care within 7 days. Hence, it is currently believed, that 7 days of treatment with C21 is a sufficient treatment duration for a conclusive first trial in this population.

Overall, the safety profile of C21 as available from preclinical data and from the phase 1 trials is interpreted as favourable for further study of the intended indication 'Treatment of COVID-19'.

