5.4.1 Withdrawal from Trial IMP

If a subject is prematurely withdrawn from IMP, the Investigator must make every effort to perform the withdrawal assessments described in Section 6.5.3, and further perform end-of-trial Visit (Visit 9) 7-10 days after the last dose of IMP.

A subject will be withdrawn from IMP if any of the following occurs:

- Need for mechanical invasive or non-invasive ventilation
- Discharge from the hospital/controlled facility
- Major protocol deviations as defined by Sponsor.

Vicore Pharma AB Version: 2.0 Trial ID: VP-C21-006 Date: 14-Aug-2020

• Sponsor decision to stop the trial or to stop the subject's participation in the trial; reasons may include medical, safety, or regulatory issues, or other reasons consistent with applicable laws, regulations, and GCP.

- It is the wish of the subject for any reason
- The Investigator judges it necessary due to medical reasons
- Adverse events such as:
 - Serious cardiovascular complications such as severe peripheral oedema or significant bradycardia indicating a potential risk for the subject as evaluated by the Investigator
 - o Moderate to severe skin rashes as judged by the Investigator e.g. Stevens-Johnson syndrome and toxic epidermal necrolysis
- Pregnancy

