6.5.4 End-of-Trial (Visit 9)

Visit 9 is performed for all randomised subjects 7-10 days after the last IMP administration and may be performed as a telephone contact.

The following procedures are performed:

- Concomitant medication
- Date of discharge
- Use of supplemental O₂
- Use of mechanical invasive and non-invasive mechanical ventilation
- Adverse events

If a subject is prematurely withdrawn from IMP, Visit 9 must be performed 7-10 days after last IMP dose (see Section 5.4.1).

Vicore Pharma AB Version: 2.0 Trial ID: VP-C21-006 Date: 14-Aug-2020

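### The oxygen endpoints have no rule for dosing that stops because of discharge, so a patient weaned and discharged on the last dosing date is scored as on oxygen through Visit 8

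*SAP*

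**What the plan says.** Protocol 5.4.1 lists "Discharge from the hospital/controlled facility" among the events that end dosing. Protocol 3.8 expects that hospitalised patients "are either discharged or taken into intensive care within 7 days", which is the length of the treatment period.

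SAP 6.10.2.5 scores time on oxygen from 0 to 7 calendar days (Visits 2 to 8). Three rules act together:

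- **Data window:** "For subjects who do not complete treatment, the assessments up to and including the day of the last study treatment administration will be considered"; the remaining days are imputed.
- **What makes an oxygen day:** "Subjects are deemed to have received oxygen where it has been administered at any time for any duration on the date of each visit".
- **Imputation:** IMP withdrawal for ventilation or death, or either event on the last dosing day, is scored as oxygen through Visit 8. Otherwise, "if a subject has missing assessments for any other reason, their last known oxygen status prior to the missing assessment will be carried forward".

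The binary endpoint in SAP 6.10.2.2 is also fixed on the last dosing day. Its Imputation paragraph again separates ventilation and death and then continues: "For subjects who withdraw from treatment for any other reason, their oxygen status on the last day of study treatment administration" is the status used. This follows protocol 13.3.1, which takes status on the last day in treatment for early withdrawals.

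At Visit 9, protocol 6.5.4 collects "Date of discharge" and supplemental oxygen use. The Summaries paragraph of SAP 6.10.2.5 states: "The number of days supplemental oxygen is required during screening, the treatment period and the follow-up period will be summarised". Neither oxygen analysis uses this later information.

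**The concern.** The two unfavourable ways of stopping early, ventilation and death, have explicit rules. The favourable one, discharge, falls into the residual category. Carry-forward from the last dosing date is then wrong in a specific way: that date counts as an oxygen day even if oxygen was stopped during it, and going home is what makes it the last dosing date.

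A patient on oxygen from Day 1 who is weaned and discharged on Day 4 therefore gets the same score, 7, as a patient on oxygen all week. A patient on oxygen daily until ventilation also scores 7. In the Wilcoxon test these patients are tied. If C21 speeds weaning, more C21 patients can be affected, and a real benefit would look smaller.

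**Working it through.** **The plan's own figure.** The documents give no effect size or power for either oxygen endpoint. The only power statement is for CRP (SAP 3: 75 per group, SD 60, difference 25, two-sided 10%). It reproduces: 25 / (60 × √(2/75)) = 2.55, and Φ(2.55 − 1.645) ≈ 0.82, or 0.815 with the noncentral t, against about 80% stated. Nothing below depends on it.

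**Error per patient.** Let d be the last dosing day, with some oxygen on day d and none afterwards, and let k ≤ d be the oxygen days up to d.

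- True oxygen days = k.
- SAP score = k + (7 − d).
- Excess = 7 − d, whatever k is.

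| Last dosing day d | 1 | 2 | 3 | 4 | 5 | 6 | 7 |
|---|---|---|---|---|---|---|---|
| Excess days | 6 | 5 | 4 | 3 | 2 | 1 | 0 |

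The score reaches 7 only if k = d, that is, with oxygen on every day from Day 1. A patient off oxygen for the whole of day d is carried forward as off, which is right if they stay off.

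**Effect on a group comparison (illustration; every input is assumed).** Let W be the day of weaning, with daily weaning chance h. For a patient on oxygen at entry, true days are T = min(W, 7), with mean (1 − (1 − h)^7)/h. This is 4.53 for h = 0.15, 3.47 for h = 0.25 and 3.06 for h = 0.30. Let q be the share of those weaned before Day 7 whose last dosing date is the weaning date; they score S = 7. Then E(7 − S) = (1 − q) × E(7 − T). If q is the same in both arms, the mean difference shrinks by the factor 1 − q.

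Power below is simulated with 75 per arm and a Wilcoxon test at two-sided 10%.

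| Scenario | q | Mean difference (days) | Power |
|---|---|---|---|
| A: all on oxygen at entry, h 0.15 v 0.25 | 0 | 4.53 − 3.47 = 1.06 | 88% |
| | 10% | 0.96 | 80% |
| | 25% | 0.80 | 67% |
| | 50% | 0.53 | 40% |
| B: 60% on oxygen at entry, h 0.15 v 0.30 | 0 | 0.6 × (4.53 − 3.06) = 0.88 | 41% |
| | 10% | 0.79 | 35% |
| | 20% | 0.71 | 29% |
| | 30% | 0.62 | 23% |
| | 50% | 0.44 | 17% |
| C: 60% on oxygen at entry, h 0.15 v 0.25 | 0 | 0.6 × 1.06 = 0.64 | 26% |
| | 10% | 0.57 | 24% |

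With equal weaning rates, the rejection rate stayed between 0.094 and 0.105, so in this model the rule creates no false positives.

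**Binary endpoint, scenario B.** The share scored as needing oxygen is 0.6 × [(1 − h)^6 + q × (1 − (1 − h)^6)].

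- At q = 0: 7% on C21 (0.6 × 0.118) and 23% on placebo (0.6 × 0.377).
- At q = 50%: 34% on C21 (0.6 × 0.559) and 41% on placebo (0.6 × 0.689).

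**The case against.** The strongest case on the other side has four parts.

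1. **The group is narrow.** The error needs oxygen at some time on the last dosing date and none afterwards. Where sites require a full day on room air before discharge, the share is near zero. Protocol 3.8 supports early discharge, not weaning and discharge on the same date. This stands and limits the size. It does not supply the missing rule.
2. **The later data may be thin.** A reader might infer that true oxygen status after the last dose is on file day by day and that the SAP overwrites it. The documents do not establish this. The withdrawal assessments in protocol 6.5.3 and Table 1 list no oxygen record. Visit 9 may be a telephone contact, and its oxygen item is not said to be dated. The follow-up day count in the SAP suggests day-level data but does not prove it. This stands and shapes the fix.
3. **An on-treatment cut-off is a legitimate choice.** Temperature and laboratory secondaries stop on the last dosing day (SAP 6.10.2.1), and the ventilation endpoints 12 hours after the last dose. A reader might conclude that not needing oxygen should be redefined by Day 7 status. That would depart from protocol 13.3.1 and is largely a choice of estimand, so it is not asked for here. Time on oxygen is different: the SAP already scores it out to Visit 8, so it has to put some value on the days after discharge.
4. **The consequence is limited.** SAP 6.10.4 treats secondary endpoints as descriptive. Daily oxygen status and discharge dates are listed, so a careful reader could spot affected patients. This is true, but the tables and tests would still carry the wrong scores.

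**Conclusion.** The gap is real. On the text, a patient who had oxygen on the last dosing date and was weaned and discharged then, or the next morning before a dose, is over-scored by 7 − d days (1 to 6) and counted as needing oxygen. This follows from the rules alone.

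The effect on the trial's results is not known. It depends on q, which the documents do not give and which may be near zero. If q is equal across arms, a true mean difference shrinks by the factor 1 − q; all power figures above rest on assumed weaning rates and oxygen use at entry. A reader might infer that early recoveries in general get the worst score, or that the trial's conclusions are at risk. Neither follows: patients off oxygen throughout the last dosing date who stay off are scored correctly, and these are descriptive secondary endpoints. The change is worth making because it is cheap and corrects a rule that mis-scores recovered patients.

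**What to change.** **SAP 6.10.2.5.** Make discharge its own imputation category. For subjects whose IMP stopped because of discharge:

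- Score days after the discharge date through Visit 8 as oxygen-free, unless Visit 9 records oxygen use after discharge.
- Keep carry-forward where Visit 9 oxygen information is missing or cannot be placed in time.
- For discharge on the morning after the last dose, state how the discharge date itself is scored. Otherwise it stays carried forward, leaving one day of excess.

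Keep the present rule as a sensitivity analysis, and leave the ventilation and death imputation unchanged.

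**SAP 6.10.2.2.** Keep the protocol's last-day-in-treatment definition as the main analysis. Add a sensitivity analysis that applies the same discharge rule. The SAP already gives both ventilation endpoints (6.10.2.3 and 6.10.2.4) sensitivity analyses that use follow-up data.

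**SAP 6.12.** List these changes. Also list a difference that is not declared now: for time on oxygen, protocol 13.3.1 assumes oxygen need for subjects withdrawing from the trial, whereas the SAP carries status forward for reasons other than ventilation or death.

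**Cost.** SAP wording and programming, settled before unblinding. Protocol 5.4 already requires the reason for IMP withdrawal to be recorded if known, and Visit 9 collects discharge date and oxygen use. The downside is that status after discharge rests on the discharge date and a Visit 9 report that may be by telephone and is not stated to be dated.
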